OR	odds ratios
SAP	statistical analysis plan
FD	free-drainage
LAR	low anterior resectio
RUV	residual urine volume
LOCF	Last Observation Carried Forward
ISR	intersphincteric resection
TCA	Turnbull-Cutait Pull-Through Coloanal Anastomosis
TaTME	total mesorectal excision
ARD	absolute risk differences
CRM	Circumferential Resection Margin
pCR	pathological complete response
DRM	Distal Resection Margin

1 Introduction

The ICCAUT trial is a single - center, prospective, two - arm, parallel - group randomized controlled study. It aims to investigate the effect of the intermittent catheter clamping combined with active urination training (ICCAUT strategy) on urinary retention and secondary catheterization after proctectomy. The aims, hypotheses, and design of the ICCAUT trial are detailed in the protocol. This statistical analysis plan (SAP) focuses on the upcoming analysis and presentation of the trial data. This SAP is based on the study protocol version 2.0. The comprehensive study design, including primary and secondary endpoints, methods for determining sample size, and the approach to data management, are essential parts of the SAP. They are crucial for understanding the trial's methodology and result interpretation.

We develop this statistical analysis plan before completing the enrollment. This helps avoid issues like selection bias in analysis methods and multiple comparisons. These issues could occur if the plan is not determined in advance.

2 Study description

2.1 Study design

The ICCAUT trial is a single - center, prospective, two - arm, parallel - group randomized controlled study. It compares intermittent catheter clamping combined with active urination training to free draining of the urinary catheter. The aim is to investigate the effect of the intermittent catheter clamping combined with active urination training (ICCAUT strategy) on urinary retention and secondary catheterization after proctectomy. Recruitment began on March 20, 2024. Patients are being recruited from the Department of Gastrocolorectal Surgery, General Surgery Center of the First Hospital of Jilin University in Changchun, Jilin Province, China. Study participants are rectal cancer patients who need low anterior resection (LAR) or abdominoperineal resection (APR). This trial was designed to enroll 400 patients by February 2026. As of the formatting of this SAP, 362 cases have been enrolled.

The trial was prospectively registered on clinicaltrial.gov (NCT06241703). The initial trial version was version 1.1.1. A minor revision was made and published in version 1.1.2 (1). Study protocol version 2.0 was updated, mainly focusing on measures to control the dropout rate and reduce bias. This SAP version 1.0 is developed based on study protocol version 2.0 and focuses on the analysis and presentation of trial data.

2.2 Treatment allocation

Patients who meet the inclusion criteria will be randomly assigned to the ICCAUT group or the free-drainage (FD) group. Stratified randomization will be performed based on the following two factors: (1) sex and (2) whether APR was performed. The allocation ratio of the ICCAUT and FD group will be 1:1.

3 Objective

3.1 Primary

The primary objective of this study is to investigate the impact of the ICCAUT strategy on urinary dysfunction in patients undergoing laparoscopic or robot - assisted proctectomy.

3.2 Secondary

The secondary objective of this study is to investigate whether the ICCAUT strategy is associated with an increased risk of postoperative urinary tract infection.

4 Endpoints

4.1 Primary Endpoint

The primary endpoint of this study is a composite endpoint. For the sake of convenience, we define this composite endpoint as urinary dysfunction in this study. It consists of incomplete bladder emptying after the first voiding following catheter removal or the need for secondary catheterization.

Incomplete bladder emptying is defined as a post-void residual urine volume (RUV) in the bladder greater than 100 ml (2–6). The method to measure RUV is detailed in the study protocol (1).

The criteria for determining the need for secondary catheterization are also detailed in the study protocol (1). Patients who undergo re-catheterization for reasons other than urinary retention will also be recorded as positive primary endpoint events. However, a sensitivity analysis will be conducted on these patients. The specific analysis method is described in the section “6.5.2.2 Sensitivity analysis for positive primary endpoints caused by reasons other than urinary retention”.

4.2 Secondary endpoints

The secondary endpoints of this study are as follows: 1) the incidence of urinary tract infections associated with the catheter, 2) the time to first void after catheter removal, 3) CRBD grade, 4) evaluation of voiding function after catheter removal using the ICIQ-SF and International Prostate Symptom Score (IPSS), 5) Evaluation of the incidence, type, and grade of complications within 30 days postoperatively, and 6) Incidence rate of residual urine volume greater than 200 ml after the first voiding.

5 Sample size

The sample size is calculated based on a differential test, with urinary dysfunction as the primary endpoint. Based on our preliminary research results, the incidence of urinary dysfunction in the bladder training group is 44.7%, and in the direct removal group, it is 59.3%. Patients are randomly assigned to the two groups in a 1:1 ratio. With a one-sided significance level α of 0.05 and a power (1- β) of 80%, the sample size was calculated using PASS 15 software. Each group, the bladder training group and the direct removal group, requires 180 cases. Assuming a dropout rate of 10%, each group requires 200 cases. Therefore, this trial needs a total of 400 cases.

6 Statistical methods

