11.1 Sample size determination

The sample size is calculated based on a differential test, with urinary dysfunction as the primary endpoint. Based on our preliminary research results, we estimate the

incidence of urinary dysfunction in the bladder training group is 44.7%, and in the direct removal group, it is 59.3%. Patients are randomly assigned to the two groups in a 1:1 ratio. With a two-sided significance level α of 0.05 and a power $(1-\beta)$ of 80%, the sample size was calculated using PASS 15 software. Each group, the ICCAUT group and the free-drainage group, requires 180 cases. Assuming a dropout rate of 10%, each group requires 200 cases. Therefore, this trial needs a total of 400 cases.

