6.1 General calculation rules

All statistical tests were 2-sided, and statistical significance was set at $P < 0.05$. All statistical analyses were performed using R or SPSS. P-values will be quoted to three decimal places. Confidence intervals (CI) will be two-sided and 95% CI will be quoted to one decimal place.

Categorical variables will be reported as frequencies and percentages. Percentages will be quoted to one decimal place. Chi-square tests in contingency tables will be replaced by Fisher's exact tests if any expected cell frequency is less than five. Absolute risk differences and the corresponding 95% CI will be calculated.

Continuous data with normal distribution were presented as mean (standard deviation) and analyzed by Student's t-test. Continuous variables with non-normal distribution were reported as medians (quartile) and compared using the Mann-Whitney U test. Hodges-Lehmann method will be used to calculate the difference in median and the corresponding 95% CI. Data will be quoted to one decimal place.

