6.5 Analysis of endpoints

6.5.1 Analysis of the primary endpoint

Categorical variables will be statistically analyzed and described using counts (percentages). Without multivariate adjustment, the primary endpoints of the two groups will be compared respectively in the ITT analysis set, the PPA set, and the ATA set. The differences between the two groups will be described using the absolute risk differences (ARD) and their 95% Confidence Intervals (95% CI). The 95% CI will be compared with an absolute risk difference of 0.

The positive primary endpoint consists of bladder residual urine volume (RUV) $>100\text{ml}$ after the first voiding or secondary catheterization within 7 days after the catheter removal. These two subtypes will also be compared between the two groups and their 95% confidence interval will be presented. Also, secondary catheterization for reasons other than urinary retention will be listed in the subsets of secondary catheterization.

Primary endpoint:

Dataset: ITT, PPA and ATA				
Variables	Free-drainage group N=***	ICCAUT group N=***	Absolute risk difference (95% CI)	P value
Urinary dysfunction	** (**)	** (**)	** (** to **)	*.***
RUV >100ml	** (**)	** (**)	** (** to **)	-
Secondary catheterization	** (**)	** (**)	** (** to **)	-
Urinary retention	** (**)	** (**)	** (** to **)	-
Not urinary retention (notes on the specific reasons)	** (**)	** (**)	** (** to **)	-
Missing data	** (**)	** (**)		

In addition, in the PPA set, the Chi-square test or Fisher's exact test will be used to analyze the variables related to the primary endpoint. Multivariate logistic regression will be employed to adjust the factors that may have an impact on the primary endpoint, and to analyze the independent risk factors affecting the primary endpoint. During this process, continuous variables will be transformed into categorical variables. The variables used for adjustment include the patient grouping in the PPA dataset (ICCAUT group/free-drainage group), tumor site (the lower edge of the tumor is above the peritoneal reflection/the lower edge of the tumor is below the peritoneal reflection), sex (male/female), and age (≤ 65 years old/ > 65 years old). In addition to the above variables, variables with a p-value < 0.1 in the univariate analysis will also be included. After adjustment, the differences between the groups will be described using the Odds Ratio (OR) and 95% CI.

Univariate analysis:

Dataset: PPA	
17 Mar 2025	SAP version 1.0

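### SAP section 5 states a one-sided 5% alpha, but its 180 per group follows only from the protocol's two-sided 5%

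*SAP*

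**What the plan says.** SAP section 5 describes a difference test of two proportions with 1:1 allocation. It assumes urinary dysfunction in 44.7% of the bladder training group and 59.3% of the direct removal group, and sets power at 80%. The alpha reads: "With a one-sided significance level α of 0.05". The result reads: "Each group, the bladder training group and the direct removal group, requires 180 cases". A 10% dropout allowance takes this to 200 per group and 400 in total.

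Protocol version 2.0, section 11.1, gives the same rates, power, software (PASS 15), 180, 200 and 400, but states "With a two-sided significance level α of 0.05". The earlier protocol version in the same file says the same. The SAP's introduction says of its source: "This SAP is based on the study protocol version 2.0".

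Elsewhere the SAP is two-sided throughout. Section 6.1 says "All statistical tests were 2-sided", with significance at P < 0.05, and adds: "Confidence intervals (CI) will be two-sided and 95% CI will be quoted to one decimal place". For the primary endpoint, section 6.5.1 says: "The 95% CI will be compared with an absolute risk difference of 0".

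**The concern.** The SAP disagrees with its parent protocol on the error rate behind the sample size, and with its own rule for testing. One-sided 5% has the same critical value as two-sided 10%, so this is a different design standard. It needs a clearly smaller trial for the same power.

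Three things are at stake. Section 5 is the SAP's only account of how the sample size was justified, and 180 cannot be reproduced from it. A reader who takes it literally would conclude that the trial was oversized. And one-sided and two-sided 5% statements in adjacent sections invite the question of which error rate the trial was designed for.

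**Working it through.** **Inputs** (SAP section 5; protocol 11.1 is identical except for sidedness): p1 = 0.447, p2 = 0.593, d = 0.146, d² = 0.021316, power 80% (z = 0.8416), 1:1 allocation. The critical value is z = 1.6449 for one-sided 0.05 and z = 1.9600 for two-sided 0.05.

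**Step 1. Reproduce the plan's 180.** The unpooled normal formula is n = (z_α + z_β)² × [p1(1−p1) + p2(1−p2)] / d². The variance term is 0.447 × 0.553 + 0.593 × 0.407 = 0.2472 + 0.2414 = 0.4885.

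- Two-sided: (1.9600 + 0.8416)² × 0.4885 / 0.021316 = 179.89, so **180**. This is the stated figure.
- One-sided: (1.6449 + 0.8416)² × 0.4885 / 0.021316 = 141.70, so **142**. This is not.

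**Step 2. Try other methods.** The pooled formula is n = [z_α√(2p̄(1−p̄)) + z_β√(p1(1−p1) + p2(1−p2))]² / d², with p̄ = 0.52. The continuity-corrected size is (n/4) × [1 + √(1 + 4/(nd))]². Sizes per group at 80% power:

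| Method | One-sided 0.05 | Two-sided 0.05 |
|---|---|---|
| Unpooled normal | 142 | 180 |
| Pooled normal | 144 | 183 |
| Arcsine | 144 | 183 |
| Log odds ratio | 146 | 186 |
| Log relative risk | 149 | 189 |
| Unpooled, continuity-corrected | 156 | 194 |
| Pooled, continuity-corrected | 158 | 197 |

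For Fisher's exact test at one-sided 0.05, full enumeration gives power of 0.798 at 156 per group and 0.802 at 157. The largest one-sided requirement is therefore 158, which is 22 below the stated 180.

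**Step 3. Check dropout.** 180/0.9 = 200 per group, as stated. The one-sided sizes become 142/0.9 = 157.8 (158), 144/0.9 = 160 and 158/0.9 = 175.6 (176). None is 200.

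**Step 4. Power at 180 per group.**

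| Test | One-sided 0.05 | Two-sided 0.05 |
|---|---|---|
| Unpooled normal | 87.6% | 80.0% |
| Pooled normal | 87.3% | 79.4% |
| Fisher's exact (enumerated) | 85.2% | 76.6% |

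At one-sided 0.05 every method puts power well above the stated 80%. At two-sided 0.05 the unpooled test matches it and the pooled test is within 0.6 percentage points.

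**The case against.** The strongest reply is that nothing in the trial depends on this word. The sample size was fixed in the protocol with the correct alpha, and 362 of 400 patients had been enrolled when the SAP was written. Sections 6.1 and 6.5.1 settle the operative test as two-sided. A reader with both documents can recover the right basis from protocol 11.1, and the 87% power arises only if that section is ignored. All of this stands, and it limits the point to an error in the stated design basis.

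A second reply is that two-sided 0.05 does not give 180 under every method. Only the unpooled formula gives it exactly. The pooled formula, which corresponds to the chi-square test named in section 6.1, needs 183, and the continuity-corrected forms need 194 and 197. The PASS option used is not stated, so the unpooled formula is an inference. That is fair, but it does not rescue the one-sided statement, which fails under every method tried.

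A deliberate change of design is not a plausible reading. The rates, power and sample size are unchanged, the protocol's revision tables list no change to section 11.1, and the SAP gives no reason for moving to a one-sided alpha.

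**Conclusion.** The concern holds. SAP section 5 is internally inconsistent: with its own rates, power and one-sided 0.05 it should give 142 to 158 per group, not 180. The protocol's two-sided 0.05 gives 180 by the unpooled normal test and 183 by the pooled test. Protocol 11.1 and SAP sections 6.1 and 6.5.1 all agree on two-sided, so one-sided is the wrong word.

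The conclusion assumes a standard comparison of two independent proportions with 1:1 allocation, as section 5 describes. It does not depend on which of the usual formulas was chosen. The error misstates the design basis; the total of 400, the conduct of the trial and the type I error of the planned analysis are unaffected. It should be corrected, but it does not threaten the trial's validity.

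**What to change.** In SAP section 5, replace one-sided with two-sided before the analysis starts, and record the change as a correction that aligns the SAP with protocol version 2.0, section 11.1. The rates, power, 180, 200 and 400 all stay. The cost is one word, with no effect on patients, conduct or the planned test. Naming the test option chosen in PASS 15 would also let a reader reproduce 180 rather than 183, but this is optional.

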6.1 General calculation rules

All statistical tests were 2-sided, and statistical significance was set at $P < 0.05$. All statistical analyses were performed using R or SPSS. P-values will be quoted to three decimal places. Confidence intervals (CI) will be two-sided and 95% CI will be quoted to one decimal place.

Categorical variables will be reported as frequencies and percentages. Percentages will be quoted to one decimal place. Chi-square tests in contingency tables will be replaced by Fisher's exact tests if any expected cell frequency is less than five. Absolute risk differences and the corresponding 95% CI will be calculated.

Continuous data with normal distribution were presented as mean (standard deviation) and analyzed by Student's t-test. Continuous variables with non-normal distribution were reported as medians (quartile) and compared using the Mann-Whitney U test. Hodges-Lehmann method will be used to calculate the difference in median and the corresponding 95% CI. Data will be quoted to one decimal place.

6.2 Analysis populations

6.2.1 Full analysis set

The comparison analysis of the primary outcome will be conducted on the basis of the "Intent-to-Treat (ITT)" analysis. The ITT analysis will include all the randomized patients and group the patients according to their randomization. In the ITT analysis, patients randomized to the ICCAUT group will be analyzed as part of the ICCAUT group. This is true even if they didn't receive any bladder training and had the catheter removed directly. Similarly, patients randomized to the Free - drainage group will be analyzed as members of the Free - drainage group, even if they ultimately received bladder training. The study needs to record the specific reasons for not following the planned procedure.

6.2.2 Per-protocol analysis set

In the per-protocol analysis set (PPA), only cases that strictly follow the randomization and the assigned treatment plan will be included in the analysis. Patients who do not receive treatment according to the assigned randomization plan

will be excluded from the PPA. The excluded patients include: 1) Patients who did not have their urinary catheters removed on the second day after surgery for various reasons, with the catheter removal time being either advanced or postponed; 2) Patients who did not carry out bladder training strictly according to the plan; 3) Patients who had to use selective α 1 adrenergic receptor blockers due to their medical conditions during their first catheterization.

6.2.3 As-treated analysis set

In the as-treated analysis set (ATA), we will analyze patients based on the actual treatment they received, rather than the treatment assigned by randomization. The ATA analysis set will include all the patients in the ITT analysis set. However, in terms of grouping, in the ATA analysis, patients who receive at least one round of bladder training are classified as the bladder training group, while those who do not receive training are classified as the direct removal group.

6.3 Missing data and its handling approaches

6.3.1 Definition of Missing Data

Since the primary endpoint is a composite endpoint, if a patient fails to achieve any of the positive events within the primary endpoint (secondary catheterization or residual urine volume > 100 ml) and any of the following situations occurs: 1) the residual urine volume after the first urination following the removal of the urinary catheter is missing; or 2) the situation of secondary catheterization within 7 days after the removal of the urinary catheter is missing, the primary endpoint will be defined as missing. The possible reasons for the missing primary endpoint include: 1) loss to follow - up or death, making it impossible to know whether secondary catheterization occurs within 7 days after the removal of the urinary catheter; 2) after the removal of the urinary catheter, due to various reasons, the bladder ultrasound for assessing the residual urine volume after the first urination is not carried out in a timely manner; 3) the patient refuses the researcher to use the data related to the patient's own micturition function.

In the case where a subject refuses the researcher to use their personal data, that

is, the subject requests to withdraw the informed consent and drop out of this study midway, all the data of this patient will be treated as missing data in the ITT analysis. If the subject refuses the collection of research data after withdrawal but consents to the collection of data before withdrawal, the researcher will treat the data after withdrawal as missing values, and the data before withdrawal can be included in the analysis.

6.3.2 Methods for handling missing data

In this study, if the missing rate of the primary endpoint is less than 5%, no imputation of missing data will be done in the analysis of the primary endpoint in the ITT, PPA, and ATA sets. During the analysis of the primary outcome, missing data will be treated as censored.

If the missing rate of the primary endpoint is 5% or higher at the end of the study, the following procedures will be adopted to handle the data with missing values in any variable of the primary endpoint.

- 1) When the data on post-void residual urine volume (RUVR) by ultrasound after the first urination is complete, and the situation of secondary catheterization within 7 days after the removal of the urinary catheter is also complete. There is no missing data.
- 2) When the data on post-void RUVR by ultrasound after the first urination is complete, but the situation of secondary catheterization within 7 days after the removal of the urinary catheter is missing.

If the post-void RUVR by ultrasound after the first urination is greater than 100 ml, handling method: The primary endpoint is reached (positive), and no imputation of missing data for secondary catheterization is performed.

If the post-void RUVR by ultrasound after the first urination is less than or equal to 100 ml, handling method: Multiple imputation method is used to impute the missing data of secondary catheterization.

3) When the data on post-void RUV by ultrasound after the first urination is missing, but the situation of secondary catheterization within 7 days after the removal of the urinary catheter is complete.

If secondary catheterization occurs within 7 days after the removal of the urinary catheter, handling method: The primary endpoint is reached (positive), and no imputation of missing data for RUV is performed.

If secondary catheterization does not occur within 7 days after the removal of the urinary catheter, and the post-void RUV by ultrasound after the second urination is not missing, handling method: The Last Observation Carried Forward (LOCF) method is used to impute the missing data of the first residual urine volume. In LOCF method, the post-void RUV after the second urination is used to impute missing data of the first post-void RUV.

If secondary catheterization does not occur within 7 days after the removal of the urinary catheter, and the post-void RUV by ultrasound after the second urination is also missing, handling method: Multiple imputation method is used to impute the missing data of the first post-void RUV.

4) When the data on post-void RUV by ultrasound after the first urination is missing, and the situation of secondary catheterization within 7 days after the removal of the urinary catheter is also missing.

If the post-void RUV by ultrasound after the second urination is not missing, handling method: The LOCF method is used to impute the missing data of the first residual urine volume. If the imputed residual urine volume is greater than 100 ml, the primary endpoint is reached (positive), and no imputation of missing data for secondary catheterization is performed; if the imputed residual urine volume is less than or equal to 100 ml, multiple imputation method is used to impute the missing data of secondary catheterization.

If the post-void RUV by ultrasound after the second urination is also missing,

handling method: Multiple imputation method is used to impute the missing data of the primary endpoint. At this time, the primary endpoint is imputed as a whole missing data, rather than imputing the RUV and secondary catheterization separately.

Through the above treatment methods, we will minimize the impact of missing data on the research results and ensure the accuracy and reliability of data analysis. The handling process of missing data in primary endpoint is shown in Figure 1.

In the analysis of secondary endpoint and subgroup analysis, we will not perform imputation of missing data.

Handling flow of missing data for primary endpoint

Both the RUV after the patient's first urination and the secondary catheterization data within 7 days after catheter removal are complete

No missing data, no processing required

The RUV after the patient's first urination is complete but the secondary catheterization data within 7 days after catheter removal is missing

The RUV after the first urination is >100 ml

The primary endpoint is achieved, and no imputation for missing data on secondary catheterization is required

The RUV after the first urination is ≤100ml

Multiple imputation method is employed to handle the missing data for secondary catheterization

The RUV after the patient's first urination is missing but the secondary catheterization data within 7 days after catheter removal is complete

Secondary catheterization occurred within 7 days after the removal of the urinary catheter

The primary endpoint is achieved, and no imputation for missing data on RUV was performed.

No secondary catheterization occurred within 7 days after the removal of the urinary catheter

The RUV after the patient's second urination is not missing

The Last Observation Carried Forward (LOCF) method is employed to impute missing data for the RUV after the first urination

The RUV after the patient's second urination is missing

Multiple imputation is used to handle the missing data for RUV after the first urination

Both the RUV after the patient's first urination and the secondary catheterization data within 7 days after catheter removal are missing

The RUV after the patient's second urination is not missing

The Last Observation Carried Forward (LOCF) method is employed to impute missing data for the RUV after the first urination

RUV is >100 ml after imputation

The primary endpoint is achieved. No imputation for missing data on secondary catheterization is needed.

RUV is ≤100 ml after imputation

Multiple imputation method is employed to handle the missing data for secondary catheterization

The RUV after the patient's second urination is also missing

Multiple imputation method is used to impute missing data for the primary endpoint (the composite event)

Figure 1 Imputation Scheme for Missing Data of the Primary Endpoint

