steering committee members before execution, with reasons provided. If the trial steering committee deems the reason valid, the order to advance or delay the catheter removal is allowed to be executed; 4) Nurses need to educate and guide enrolled patients to ensure that patients in the bladder training group actively perform forceful urination during each period of unclamping to assist in urine discharge; 5) Patients in the bladder training group, if unable to persist in reaching the specified catheter clamping time (less than 3 hours of catheter clamping before feeling the urge to urinate), may end a training cycle early, open the catheter for 5 minutes, and then start the next clamping training cycle; 6) Before catheter removal, patients in the bladder training group must complete the Bladder Training Quality Self-Assessment Form; 7) During the first catheterization of the patient, selective α 1-adrenergic receptor blockers (such as Tamsulosin) should not be used. If it is necessary to use them due to the patient's condition, the reasons should be recorded; 8) Each patient enrolled in the study will be given a subject compensation of 100 yuan to increase the compliance of the enrolled patients and the success rate of follow-up.

(3) Endpoint quality control

Our project team requires all levels of physicians in our department to strictly follow the bladder residual urine assessment method and the criteria for secondary catheterization as stipulated in the project research plan to calculate bladder residual urine and decide whether to perform secondary catheterization. To reduce bias in the measurement of bladder residual urine, this study implements quality control in the following two aspects: 1) A fixed radiologist is responsible for assessing bladder residual urine, and this physician has specialized in abdominal digestive and urinary system ultrasound examinations for over 10 years; 2) The ultrasound diagnosis location is set in the same therapeutic area as the patient, ensuring that patients can undergo immediate ultrasound examination after the first urination following catheter removal, avoiding the impact on the judgment of residual urine due to a long interval between urination and ultrasound examination; 3) For patients who fail to undergo the residual urine volume assessment in a timely manner for various reasons after the first urination, a bladder ultrasound should be conducted immediately after the second

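### Below 5% missing, the primary analysis keeps partly observed patients who are positive and appears to exclude those who are so far negative; this inflates event rates and can shift the difference if missingness is uneven

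*SAP*

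**What the plan says.** The primary endpoint is a composite: residual urine above 100 ml after the first void, or re-catheterisation within 7 days. SAP 6.3.1 makes it missing only "if a patient fails to achieve any of the positive events within the primary endpoint" and either component is unrecorded. One observed positive component therefore settles the patient as an event, whatever is missing on the other.

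SAP 6.3.2 then splits on the overall missing rate:

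- **Below the threshold:** "if the missing rate of the primary endpoint is less than 5%, no imputation of missing data will be done", in all three analysis sets, and "During the analysis of the primary outcome, missing data will be treated as censored".
- **At 5% or more:** the same so-far-negative patients are kept. A second-void residual replaces a missing first one; failing that, imputation is used. For a first residual of 100 ml or less with unknown catheter status, "Multiple imputation method is used to impute the missing data of secondary catheterization".

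Protocol version 2.0, section 11.3, repeats these rules.

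Three other provisions matter:

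- SAP 6.2.1: "The ITT analysis will include all the randomized patients".
- Protocol version 2.0, section 10(3): if the first scan is missed, "a bladder ultrasound should be conducted immediately after the second" urination.
- SAP 6.5.2.1: ITT sensitivity analyses set all missing endpoints to positive, then all to negative, whether or not the 5% threshold is reached.

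SAP 6.5.1 compares the arms by an unadjusted absolute risk difference. No time-to-event method is planned.

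**The concern.** A binary outcome analysed by risk difference has no censoring mechanism, so the instruction most naturally means that these patients leave the analysis. Among the partly observed, whether a patient leaves depends on the result of the component that was seen: positives stay and negatives go. That is selection on outcome within the primary analysis. It also conflicts with the all-randomised ITT set, which version 2.0 adopted, according to its change table, to avoid selection bias.

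Two features add to this. The trigger is one overall missing rate with no check by arm, so uneven missingness can pass under it. And the second-void scan, introduced as a remedy for missing endpoints, is not used below 5%. A patient with a first scan missed, a second-void residual recorded and no re-catheterisation is kept if 5% of endpoints are missing and lost at 4.9%.

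At stake are the reported event rates and, if missingness differs between arms, the treatment difference.

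**Working it through.** **Plan figures.** Planning rates are 44.7% (ICCAUT) and 59.3% (free drainage), a difference of 14.6 points (protocol version 2.0, 11.1; SAP 5). With two-sided α 0.05, 80% power and unpooled variance, n = (1.960 + 0.842)² × (0.447×0.553 + 0.593×0.407) / 0.146² = 179.9, so 180 per arm. Then 180/0.9 = 200 per arm and 400 in total, as the protocol states. Under 5% of 400 means at most 19 missing endpoints (4.75%).

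**Formula.** For one arm let p be the true event rate, v the probability that the observed component is already positive, and q the share of patients with the other component missing at random. The share dropped is d = q(1−v). Under exclusion:

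- analysed rate = [(1−q)p + qv] / (1−d)
- excess over p = qv(1−p) / (1−d) = d·v(1−p) / [(1−v)(1−d)]

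The excess is positive whenever v > 0. Patients with both components missing do not contribute to it.

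**Assumptions, not in the documents.** Catheter status is the missing component, and 80% or 95% of events show as residual above 100 ml, so v = 0.80p or 0.95p. The dropped shares average 4.9%, just under the trigger.

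**Example.** Free drainage, 95%, 4.9% dropped: v = 0.95×0.593 = 0.5634; excess = 0.049×0.5634×0.407 / (0.4366×0.951) = 0.0271, or 2.7 points.

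In the table, the difference is free drainage minus ICCAUT and shifts are from 14.6 points, computed before rounding.

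| Dropped, ICCAUT / free drainage | Events seen on residual | ICCAUT rate (%) | Free-drainage rate (%) | Difference | Shift | Shift, all-negative row | Shift, all-positive row |
|---|---|---|---|---|---|---|---|
| 4.9% / 4.9% | 80% | 46.29 | 61.19 | 14.91 | +0.31 | −0.42 | −0.42 |
| 4.9% / 4.9% | 95% | 46.80 | 62.01 | 15.20 | +0.60 | −0.14 | −0.14 |
| 3.3% / 6.5% | 80% | 45.75 | 61.85 | 16.10 | +1.50 | −1.01 | +2.19 |
| 3.3% / 6.5% | 95% | 46.09 | 62.95 | 16.86 | +2.26 | −0.31 | +2.89 |
| 6.5% / 3.3% | 80% | 46.84 | 60.55 | 13.71 | −0.89 | +0.16 | −3.04 |
| 6.5% / 3.3% | 95% | 47.54 | 61.09 | 13.55 | −1.05 | +0.03 | −3.17 |

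With even dropping, inflation is 1.6-2.7 points per arm (1.5-2.6 at 19 of 400) and the difference moves by 0.3-0.6.

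**Only the residual missing.** The observed component is then re-catheterisation. Taking it to mark the other 5-20% of events (no overlap between components) and 4.9% dropped, the excess is 0.1-0.3 points.

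**Patients kept in N instead.** They would count as non-events, as in the all-negative row. At 4.9% per arm the rates become 44.0-44.5% and 58.2-59.0%, so event rates are understated.

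**Check of the remedy.** Twenty thousand trials per scenario were simulated with 200 per arm, v = 0.5p and 9.5% expected to be dropped, all in one arm. This is a stress test, not a forecast. Exclusion gave a mean difference (ICCAUT minus free drainage) of −13.0 or −16.4 points, depending on the arm. Imputing the so-far-negative patients from completely observed ones in the same arm returned −14.6.

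**The case against.** Complete-case analysis under 5% missing, backed by extreme-case analyses, is a common and defensible choice. Much of that defence stands.

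- **The plan has a safeguard.** A reader might infer that nothing in the plan addresses the problem below 5%. That is not so: the all-positive and all-negative rows apply there too. In the catheter-status scenario only 4-7% of dropped patients are hidden events if 95% of events show on the residual (14-23% if 80%), so the all-negative row lies close to the truth. But these rows leave the primary estimate as it is, ignore the second-void data, and do not include the Figure 1 scheme.
- **Exclusion is an inference.** The SAP 6.5.1 table shell has a missing-data row but does not say whether percentages use all randomised patients. A reader might take deletion as certain; the text leaves it open, and the other reading reverses the bias in the rates.
- **Large shifts need implausible inputs.** A reader might infer a distortion of 3 to 5 points. The formula does give −3.4 to +4.7 with 1.0% against 8.8% dropped. At the upper end, however, that requires catheter status to be missing in 17-20% of free-drainage patients and about 2% of ICCAUT patients. If 19 missing endpoints fell between arms by chance, a split of 2 to 17 or worse has two-sided probability 2×(1+19+171)/2¹⁹ ≈ 0.0007. The protocol has 7-day observation, daily endpoint checks by the coordinator and contact to 30 days. Patients and nurses are unblinded and patients may refuse endpoint follow-up, so some imbalance is possible, but nothing in the documents points to one of that size.
- **Even 4.9% is demanding.** It needs catheter status missing in about 8-11% of each arm.

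**Conclusion.** The point holds as a defect in the rule, with a modest expected effect. The text retains partly observed positives and leaves so-far-negative patients unimputed under a term that is undefined for this endpoint. Read as exclusion, that is outcome-dependent selection, contrary to the stated ITT set.

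Under the assumptions shown, each arm's event rate is overstated by about 1.6-2.7 points at the limit of the trigger, while the treatment difference moves by less than 1 point if equal shares are dropped. At 3.3% against 6.5% it moves by −1.1 to +2.3 points. If only residual volumes are missing, the inflation is about 0.1-0.3 points.

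The direction of the inflation is certain only for missingness at random and for the exclusion reading. The documents do not give the split of events between components or any expected pattern of missingness, so these figures are illustrations. They do not show that the trial's conclusion would change. The rule should be corrected before analysis because a better one is already in the SAP.

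**What to change.** In SAP 6.3.2 and 6.5.2.1, and in the matching protocol text:

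1. Remove the 5% trigger and the word censored.
2. Apply the Figure 1 scheme to the primary ITT analysis at any missing rate: second-void residual where recorded, otherwise multiple imputation.
3. State that the denominator is all randomised patients, and say how the missing-data row relates to N.
4. Report missingness by arm and by component.
5. Show complete cases as a sensitivity row beside the two extreme-case rows.

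The decision scheme is already written, but the imputation is not fully specified: the SAP gives no model, predictors, number of imputations or method of pooling the risk difference. These must be added, and the procedure run even for a handful of patients. A second cost is that second-void values will stand in for some first-void values in the primary analysis; the complete-case row lets readers see how much that matters. No new data collection is needed.
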